### **6.1. Adverse Events**

#### **6.1.1. Adverse Event Dictionary**

AEs will be coded using the current version of MedDRA® (Medical Dictionary for Regulatory Activities). In MedDRA, each verbatim term is mapped to a preferred term (PT) and high level term (HLT), which is then mapped to a system organ class (SOC). Tables and listings will present data at the SOC and PT level.

#### **6.1.2. Adverse Event Severity and Toxicity Grading**

Adverse events will be graded by the investigators as Grade 1 (mild), Grade 2 (moderate), Grade 3 (severe), or Grade 4 (life-threatening) according to toxicity criteria specified in the study protocol. The severity grade of AEs for which the investigator did not record severity will be categorized as "missing" for tabular summaries and data listings.

#### **6.1.3. Relationship of Adverse Events to Study Drug**

The investigators will evaluate whether an AE is related to study drug. Related AEs are those for which 'Related' was marked for the question 'Related to the study drug' in the eCRF. Events for which the investigator did not record relationship to study drug will be considered as related to study drug in AE summary tables and will be shown as missing in AE listings.

#### **6.1.4. Relationship of Adverse Events to Study Procedure**

The investigators will also evaluate whether an AE is related to study procedure. Related AEs are those for which 'Yes' was marked for question 'Related to the study procedure' in the eCRF. Events for which the investigator did not record relationship to study procedure will be shown as missing in AE listings.

### **6.1.5. Serious Adverse Events**

Serious adverse events (SAEs) are those identified in the eCRF where ‘Yes’ was marked for the question ‘Serious’. Serious AEs are captured in both the eCRF database (clinical database) and the SAE database (managed by Gilead Pharmacovigilance and Epidemiology). The two databases will be reconciled before database finalization.

### **6.1.6. Treatment-Emergent Adverse Events**

#### **6.1.6.1. Definition of Treatment-Emergent**

Treatment-emergent AEs are defined as events that meet one of the following criteria:

- Any AEs with onset date of on or after the study drug start date and no later than 30 days after permanent discontinuation of study drug or
- Any AEs leading to premature discontinuation of study drug

#### **6.1.6.2. Incomplete Dates**

If the onset date of the AE is incomplete and the AE stop date is not prior to the first dosing date of study drug, then the month and year (or year alone if month is not recorded) of onset determine whether an AE is treatment emergent. The event is considered treatment emergent if both of the following 2 criteria are met:

- The AE onset is the same as or after the month and year (or year) of the date of first dose of study drug, and
- The AE onset date is the same as or before the month and year (or year) of the date corresponding to 30 days after the date of the last dose of study drug

An AE with completely missing onset and stop dates, or with the onset date missing and a stop date later than the date of the first dose of study drug, will be considered to be treatment emergent. In addition, an AE with the onset date missing and incomplete stop date with the same or later month and year (or year alone if month is not recorded) as the first dosing date of study drug will be considered treatment emergent.

### **6.1.7. General Considerations for Analyses**

Additional considerations for AE summaries and calculations are as follows when a subject has multiple occurrence of an AE at the level of the PT:

- Multiple events (by PT) will be counted once only per subject
- For summaries by severity grade, the most severe event will be selected per subject

### **6.1.8. Summaries of Adverse Events**

In summary tables, SOC will be presented alphabetically and events within SOC will be presented by decreasing frequency count, based on the total number of events by hepatic function group. For each SOC and PT, the number and percentage of subjects reporting an event will be calculated by hepatic function group.

### **6.1.9. Additional Analysis of Adverse Events**

No additional analyses of AEs are planned.

## **6.2. Clinical Laboratory Evaluations**

A baseline/predose value is defined as the last available measurement obtained prior to administration of the first dose of study drug. In the case where no assessment is available at the baseline visit, the screening assessment will be used. This baseline/predose value will be used as the basis for change from baseline/predose.

A post-dose measurement is defined as any value obtained after the first dose of study drug.

### **6.2.1. General Considerations for Analyses of Laboratory Data**

Listings of laboratory reference ranges and individual subject laboratory results will be provided.

A listing of subjects with graded laboratory results will be provided. This listing will include the complete laboratory test profile for each parameter with a graded result throughout the study.

For summaries of laboratory values (predose, postdose, change from predose), only values obtained at the scheduled visits will be included.

For summaries of laboratory abnormalities, all postdose values will be considered in determining the maximum toxicity grade.

Summaries of clinical laboratory data will be provided for subjects in the safety analysis set. Analysis will be based on values reported in conventional units. No inferential statistics will be provided.

### **6.2.2. Summaries of Laboratory Results**

Chemistry and hematology laboratory tests will be summarized by hepatic function group using descriptive statistics (sample size, mean, SD, median, Q1, Q3, minimum, and maximum) for predose assessments, postdose assessments, and change from predose assessments.

In the case of multiple values in an analysis window, data will be selected for analysis as described in Section 3.8.3. See Section 3.6 for details on missing data, and see Section 3.8 for details on analysis windows for these data.

### **6.2.3. Laboratory Abnormality Grades**

For specified clinical chemistry, hematology, and urinalysis tests, the criteria described in the study protocol will be used to grade laboratory results as missing (no grade), mild (Grade 1), moderate (Grade 2), severe (Grade 3) or possibly life-threatening (Grade 4). “No Grade” includes all values that do not meet criteria for an abnormality of at least grade one. Some lab tests have criteria for both increased and decreased levels; analysis for each direction (i.e., increased, decreased) will be presented separately.

If there is any lab toxicity grading scale overlapping with normal reference ranges (e.g., Grade 1 scale overlaps with normal reference ranges), lab values within the normal range will still be graded with a footnote indicating the number of graded subjects in such a situation.

Laboratory abnormalities may be reported as an adverse event, and the clinical grading of an event may be different from the quantitative grading depending on the clinical status and underlying conditions.

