8.1.3. Secondary Endpoint

The secondary endpoints are the incidences of adverse events and laboratory abnormalities.

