8.5.3. Laboratory Evaluations

Selected laboratory data (clinical chemistry and hematology) will be summarized using only observed data. Absolute values and change from predose at all scheduled time points will be summarized.

Laboratory abnormalities will be graded using GSI Grading Scale for Severity of Adverse Events and Laboratory Abnormalities ([Appendix 4](#)) for analysis purposes.

Incidence of treatment-emergent laboratory abnormalities, defined as values that increase at least one toxicity grade from predose at any time postdose up to the completion of study follow-up, will be summarized. If predose data are missing, then any graded abnormality (ie, at least a Grade 1) will be considered treatment emergent.

Laboratory abnormalities that occur before the first dose of investigational medicinal product or after the completion of study follow-up will be included in a data listing.

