Appendix 4. GSI Grading Scale for Severity of Adverse Events and Laboratory Abnormalities

Version: 18 June 2012

HEMATOLOGY				
	Grade 1	Grade 2	Grade 3	Grade 4
Hemoglobin HIV POSITIVE Adult and Pediatric ≥ 57 Days	8.5 to 10.0 g/dL 85 to 100 g/L	7.5 to < 8.5 g/dL 75 to < 85 g/L	6.5 to < 7.5 g/dL 65 to < 75 g/L	< 6.5 g/dL < 65 g/L
HIV NEGATIVE Adult and Pediatric ≥ 57 Days	10.0 to 10.9 g/dL 100 to 109 g/L OR Any decrease from Baseline 2.5 to < 3.5 g/dL 25 to < 35 g/L	9.0 to < 10.0 g/dL 90 to < 100 g/L OR Any decrease from Baseline 3.5 to < 4.5 g/dL 35 to < 45 g/L	7.0 to < 9.0 g/dL 70 to < 90 g/L OR Any decrease from Baseline ≥ 4.5 g/dL ≥ 45 g/L	< 7.0 g/dL < 70 g/L
Infant, 36–56 Days (HIV POSITIVE OR NEGATIVE)	8.5 to 9.4 g/dL 85 to 94 g/L	7.0 to < 8.5 g/dL 70 to < 85 g/L	6.0 to < 7.0 g/dL 60 to < 70 g/L	< 6.0 g/dL < 60 g/L
Infant, 22–35 Days (HIV POSITIVE OR NEGATIVE)	9.5 to 10.5 g/dL 95 to 105 g/L	8.0 to < 9.5 g/dL 80 to < 95 g/L	7.0 to < 8.0 g/dL 70 to < 80 g/L	< 7.0 g/dL < 70 g/L
Infant, 1–21 Days (HIV POSITIVE OR NEGATIVE)	12.0 to 13.0 g/dL 120 to 130 g/L	10.0 to < 12.0 g/dL 100 to < 120 g/L	9.0 to < 10.0 g/dL 90 to < 100 g/L	< 9.0 g/dL < 90 g/L
Absolute Neutrophil Count (ANC) Adult and Pediatric, > 7 Days	1000 to 1300/mm ³ 1.00 to 1.30 GI/L	750 to < 1000/mm ³ 0.75 to < 1.00 GI/L	500 to < 750/mm ³ 0.50 to < 0.75 GI/L	< 500/mm ³ < 0.50 GI/L
Infant, 2 – ≤ 7 Days	1250 to 1500/mm ³ 1.25 to 1.50 GI/L	1000 to < 1250/mm ³ 1.00 to < 1.25 GI/L	750 to < 1000/mm ³ 0.75 to < 1.00 GI/L	< 750/mm ³ < 0.75 GI/L
Infant, 1 Day	4000 to 5000/mm ³ 4.00 to 5.00 GI/L	3000 to < 4000/mm ³ 3.00 to < 4.00 GI/L	1500 to < 3000/mm ³ 1.50 to < 3.00 GI/L	< 1500/mm ³ < 1.50 GI/L

HEMATOLOGY				
	Grade 1	Grade 2	Grade 3	Grade 4
Absolute CD4+ Count HIV NEGATIVE ONLY Adult and Pediatric > 13 Years	300 to 400/mm ³ 300 to 400/μL	200 to < 300/mm ³ 200 to < 300/μL	100 to < 200/mm ³ 100 to < 200/μL	< 100/mm ³ < 100/μL
Absolute Lymphocyte Count HIV NEGATIVE ONLY Adult and Pediatric > 13 Years	600 to 650/mm ³ 0.60 to 0.65 GI/L	500 to < 600/mm ³ 0.50 to < 0.60 GI/L	350 to < 500/mm ³ 0.35 to < 0.50 GI/L	< 350/mm ³ < 0.35 GI/L
Platelets	100,000 to < 125,000/mm ³ 100 to < 125 GI/L	50,000 to < 100,000/mm ³ 50 to < 100 GI/L	25,000 to < 50,000/mm ³ 25 to < 50 GI/L	< 25,000/mm ³ < 25 GI/L
WBCs	2000/mm ³ to 2500/mm ³ 2.00 GI/L to 2.50 GI/L	1,500 to < 2,000/mm ³ 1.50 to < 2.00 GI/L	1000 to < 1,500/mm ³ 1.00 to < 1.50 GI/L	< 1000/mm ³ < 1.00 GI/L

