- Toxicity grades for Quantitative and Dipstick Hematuria will be assigned by Covance Laboratory, however for other laboratories, toxicity grades will only be assigned to Dipstick Hematuria.
- With the exception of lipid tests, any graded laboratory test with a result that is between the LLN and ULN should be assigned Grade 0.
- If the severity of a clinical AE could fall under either one of two grades (e.g., the severity of an AE could be either Grade 2 or Grade 3), select the higher of the two grades for the AE.

CARDIOVASCULAR				
	Grade 1	Grade 2	Grade 3	Grade 4
Cardiac Arrhythmia (general) (By ECG or physical exam)	Asymptomatic AND No intervention indicated	Asymptomatic AND Non-urgent medical intervention indicated	Symptomatic, non-life-threatening AND Non-urgent medical intervention indicated	Life-threatening arrhythmia OR Urgent intervention indicated
Cardiac-ischemia/ Infarction	NA	NA	Symptomatic ischemia (stable angina) OR Testing consistent with ischemia	Unstable angina OR Acute myocardial infarction
Hemorrhage (significant acute blood loss)	NA	Symptomatic AND No transfusion indicated	Symptomatic AND Transfusion of ≤ 2 units packed RBCs (for children ≤ 10 cc/kg) indicated	Life-threatening hypotension OR Transfusion of > 2 units packed RBCs indicated (for children ≤ 10 cc/kg) indicated
Hypertension (with repeat testing at same visit)	140–159 mmHg systolic OR 90–99 mmHg diastolic	> 159–179 mmHg systolic OR > 99–109 mmHg diastolic	> 179 mmHg systolic OR > 109 mmHg diastolic	Life-threatening consequences (eg, malignant hypertension) OR Hospitalization (other than ER visit) indicated
Pediatric ≤ 17 Years (with repeat testing at same visit)	NA	91st–94th percentile adjusted for age, height, and gender (systolic and/or diastolic)	≥ 95th percentile adjusted for age, height, and gender (systolic and/or diastolic)	Life-threatening consequences (eg, malignant hypertension) OR Hospitalization indicated (other than emergency room visit)
Hypotension	NA	Symptomatic, corrected with oral fluid replacement	Symptomatic, IV fluids indicated	Shock requiring use of vasopressors or mechanical assistance to maintain blood pressure
Pericardial Effusion	Asymptomatic, small effusion requiring no intervention	Asymptomatic, moderate or larger effusion requiring no intervention	Effusion with non-life-threatening physiologic consequences OR Effusion with nonurgent intervention indicated	Life-threatening consequences (eg, tamponade) OR Urgent intervention indicated

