### **2.3. Changes from Protocol-Specified Analysis**

No changes from protocol-specified analyses are planned.

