### **6.2.4. Treatment-Emergent Graded Abnormalities**

A treatment-emergent graded laboratory abnormality is defined as an increase of at least 1 toxicity grade from the predose assessment and occurring after the predose visit and on or before the date of the last dose of the treatment plus 30 days. If the predose assessment is missing, then any abnormality of at least Grade 1 will be considered a treatment-emergent graded laboratory abnormality.

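### For non-lipid tests whose grade limits can overlap the normal range, the SAP grades in-range laboratory values that the protocol's scale sets to Grade 0, and declares no change

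*SAP*

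**What the plan says.** Protocol 8.5.3 fixes the scale for analysis: "Laboratory abnormalities will be graded using GSI Grading Scale for Severity of Adverse Events and Laboratory Abnormalities", with a reference to Appendix 4. The notes in Appendix 4 settle what happens when a grade band and the reference range overlap: "With the exception of lipid tests, any graded laboratory test with a result that is between the LLN and ULN should be assigned Grade 0".

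SAP 6.2.3 first adopts the protocol's criteria. It then treats overlap in the opposite way: "lab values within the normal range will still be graded with a footnote indicating the number of graded subjects in such a situation". It does not separate lipid from non-lipid tests. SAP 2.3 states: "No changes from protocol-specified analyses are planned".

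The grades feed an endpoint. Protocol 8.1.3 reads: "The secondary endpoints are the incidences of adverse events and laboratory abnormalities". SAP 6.2.4 defines a treatment-emergent abnormality as "an increase of at least 1 toxicity grade from the predose assessment" within the postdose period, and SAP 6.2.5 tabulates its incidence by hepatic function group.

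**The concern.** A programmer cannot follow both documents for a non-lipid result that lies inside the reference range and also meets a grade criterion. The SAP directs the programmer to grade it, and the scale the SAP says it is using directs Grade 0. Because SAP 2.3 reports no change, nothing tells the reader of the study report that the laboratory table departs from the protocol.

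What is at stake is the laboratory half of the secondary endpoint. Treatment emergence depends on the difference between two grades, so the in-range rule matters at predose as well as postdose, and an error at either end changes whether the subject is counted. The groups are small, so a single subject is visible in the percentages.

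**Working it through.** The plan states no figure for this rule, so there is nothing to reproduce. The check has three parts.

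**1. Which tests can be affected.** In Appendix 4, Grade 1 for AST, ALT, GGT, alkaline phosphatase, bilirubin, PT, INR and APTT starts above a multiple of ULN, and Grade 1 for albumin starts below LLN. Grade 1 for these tests cannot overlap the range. Two kinds of criterion can:
- fixed cut-offs, such as fasting glucose, where Grade 1 is 110 to 125 mg/dL whatever the laboratory's ULN;
- change-from-baseline criteria, such as haemoglobin (HIV-negative adults), where Grade 1 includes "Any decrease from Baseline 2.5 to < 3.5 g/dL" whatever the resulting value.

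Lipid tests are exempt from the Grade 0 note, so for them the SAP and the protocol agree.

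**2. The two rules applied to the same values.** The reference limits and subject values are assumptions, since the documents give no ranges. A change counts as treatment-emergent if postdose grade minus predose grade is at least 1.

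| Test, predose to postdose | Assumed limit | SAP 6.2.3 | Appendix 4 note |
|---|---|---|---|
| Fasting glucose 100 to 112 mg/dL | ULN 115 | Grade 0 to 1: counted | Grade 0 to 0: not counted |
| Fasting glucose 112 to 120 mg/dL | ULN 115 | Grade 1 to 1: not counted | Grade 0 to 1: counted |
| Haemoglobin 16.0 to 13.4 g/dL | LLN 12.0 to 13.0 | Grade 0 to 1: counted | Grade 0 to 0: not counted |
| Haemoglobin 16.0 to 13.4 g/dL | LLN 13.5 | Grade 0 to 1: counted | Grade 0 to 1: counted |

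The haemoglobin fall is 16.0 − 13.4 = 2.6 g/dL, which lies in the 2.5 to < 3.5 band. The value 13.4 is above the absolute Grade 1 band, so only the change criterion applies. With a glucose ULN of 110 or lower, the two rules agree in both glucose rows. The first and third rows are over-counts by the SAP, and the second is an under-count. Whether any of this occurs depends on the laboratory's limits.

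**3. Weight of one subject.** SAP Section 6 summarises safety data by hepatic function group within cohort, and neither that section nor SAP 6.2.5 splits laboratory abnormalities by smoking status. The planned numbers are in protocol 3.1:
- Cohort 1: 20 impaired and 20 controls, so 1/20 = 5 percentage points;
- Cohorts 2 and 3: 10 impaired and up to 10 controls each, so 1/10 = 10 points.

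These are planned numbers. The actual denominator in SAP 6.2.5 is subjects with postdose values.

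For orientation only, let p be the share of subjects who are graded solely because of the SAP rule. The chance of at least one in a group of n is 1 − (1 − p)^n. The values of p are assumptions:

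| p | n = 10 | n = 20 |
|---|---|---|
| 2% | 1 − 0.98^10 = 18% | 1 − 0.98^20 = 33% |
| 5% | 1 − 0.95^10 = 40% | 1 − 0.95^20 = 64% |
| 10% | 1 − 0.90^10 = 65% | 1 − 0.90^20 = 88% |

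The documents do not say where p lies, and it may be zero.

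**The case against.** The strongest reply is that little depends on this. The SAP clause acts only where a scale overlaps the range, and the main liver-related scales cannot. SAP 6.2.1 excludes inferential statistics for laboratory data, so no test, power figure or pharmacokinetic conclusion is touched. The SAP footnotes the number of subjects graded in range and lists reference ranges, individual results and full profiles for graded parameters, so a careful reader could re-grade. All of this stands, and it limits the weight of the point. It does not remove the conflict: the footnote leaves the percentage as it is, and it does not restore a subject whose predose grade hid a later rise.

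One could also read the SAP's overlap clause as covering fixed bands only. The haemoglobin example would then drop out, but the fixed cut-offs would remain.

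Several stronger readings are tempting but are not supported:
- *A reader might infer that the protocol forbids grading any in-range value.* It exempts lipids.
- *That the inflation falls mainly on healthy controls and shrinks the contrast.* Impaired subjects can also have normal glucose or haemoglobin at entry, and the error can go either way.
- *That the decision to open Cohorts 2 and 3 is affected.* Protocol 3.1 lists treatment-emergent laboratory abnormalities among its inputs, but SAP Section 1 limits the SAP to the study report's outputs. Nothing says the cohort review uses the SAP grading.
- *That the 10 + 18 + 2 + 1 = 31 scheduled PK samples make large haemoglobin falls likely.* No blood volumes are given. At an assumed 4 to 6 mL each, 31 samples total 124 to 186 mL, which is 2.5 to 3.7% of an assumed 5 L. In full proportion that is about 0.4 to 0.6 g/dL from 15.5, well short of 2.5. Safety bloods would add to this by an unstated amount.
- *That one subject moves every group by 10 to 12.5 points.* The 8 per group behind 12.5 is the evaluable number for the PK sample size, and Cohort 1 safety groups are planned at 20.

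**Conclusion.** The conflict between SAP 6.2.3 and the Appendix 4 note is plain, present in both documents and undeclared. It is confined to non-lipid tests with fixed or change-from-baseline criteria that overlap the laboratory's range. There, the treatment-emergent incidence can be too high or too low. The number of affected subjects and the net direction cannot be determined without reference ranges. What follows from the planned numbers is about 5 percentage points per subject in Cohort 1 and about 10 in Cohorts 2 and 3 if they open. The numerical examples rest on assumed limits and show only that the two rules can differ. The primary endpoints are unaffected. It should be corrected because a stated endpoint would otherwise be tabulated by a rule that differs from the protocol's without saying so.

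**What to change.** Replace the overlap sentence in SAP 6.2.3 with the Appendix 4 rule: non-lipid results between LLN and ULN are Grade 0, lipid results are graded by their bands, and this applies at predose and postdose for all grading and treatment-emergent summaries. The in-range footnote would then be needed only for lipids.

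If the sponsor prefers to grade in-range values, record and justify that in SAP 2.3 and reconcile the Appendix 4 note with it.

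The first option costs one sentence in the SAP and one condition in the grading program, with no new data. It should be settled before the SAP is finalised.

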### **6.2.4. Treatment-Emergent Graded Abnormalities**

A treatment-emergent graded laboratory abnormality is defined as an increase of at least 1 toxicity grade from the predose assessment and occurring after the predose visit and on or before the date of the last dose of the treatment plus 30 days. If the predose assessment is missing, then any abnormality of at least Grade 1 will be considered a treatment-emergent graded laboratory abnormality.

### **6.2.5. Summaries of Graded Laboratory Abnormalities**

The incidence of treatment-emergent graded laboratory abnormalities (number and percentage of subjects) will be presented by hepatic function group. Only the maximum postdose abnormality grade (by each laboratory test or overall as appropriate) observed will be counted. The denominator is the number of subjects with non-missing postdose values in the given analysis window.

## **6.3. Vital Signs**

Each vital signs measurement (including temperature, pulse, systolic blood pressure, diastolic blood pressure, and respiration rate) and weight measurement will be summarized by hepatic function group using descriptive statistics (sample size, mean, SD, median, Q1, Q3, minimum, and maximum) for predose, postdose, and change from predose assessments.

In case of multiple values observed in an analysis window, data will be selected for analysis as described in Section 3.8.3. See Section 3.6 for details on missing data, and see Section 3.8 for details on analysis windows for these data.

A listing of individual subject vital signs will be provided including cohort, hepatic function group, assessment date, temperature, pulse, blood pressures, respiration rate, and weight.

#### **6.4. Electrocardiogram (ECG) Results**

Safety ECG results (i.e., normal, not clinically significant abnormal, and clinically significant abnormal) in each postdose visit will be summarized (number) by predose safety ECG result and hepatic function group.

A listing of safety ECG results will be provided including cohort, hepatic function group, assessment date and time, and safety ECG result.

